14.0 ADVERSE REACTIONS DEFINITIONS AND REPORTING REQUIREMENTS

All adverse events that occur, starting from the time of the first treatment, will be recorded in the source documents and Case Report Forms (CRF).

Adverse Events (AE) occurring will be captured and followed until the condition resolves, stabilizes, is otherwise explained, or the subject is lost to follow-up. Subjects will be instructed that they may contact the Investigator at any time throughout the course of the study.

The Investigator and/or designated study staff will review each event and assess its relationship to the study device (not related, unlikely, possible, probable, and highly probable). The following definitions will be used for rating relationship to the SoftWave treatments:

- Not related – The event is clearly related to other factors such as the subject's clinical state, therapeutic interventions, or concomitant medications administered to the subject.
- Unlikely – The event was most likely produced by other factors such as the subject's clinical state, therapeutic interventions, or a concomitant medication administered to the subject; and does not follow a known response pattern to the investigational product.
- Possible – The event follows a reasonable temporal sequence from the time of investigational product administration; **and/or** follows a known response pattern to the study sampling sessions; **but** could have been produced by other factors such as the subject's clinical state, therapeutic interventions, or concomitant medications administered to the subject.
- Probable – The event follows a reasonable temporal sequence from the time of investigational product administration; **and** follows a known response pattern to the investigational product; **and** cannot be reasonably explained by other factors such as the subject's clinical state, therapeutic interventions, or concomitant medications administered to the subject.
- Highly Probable – The event follows a reasonable temporal sequence from the time of investigational product administration; **and** follows a known response pattern to the investigational product; **and** cannot be reasonably explained by other factors such as the subject's clinical state, therapeutic interventions, or concomitant medications administered to the subject; **and** either occurs immediately following investigational product administration, **or** improves on stopping the investigational product, **or** reappears on repeat exposure, **or** there is a positive reaction at the application site.

Each adverse event reported will be graded on a 3-point severity. Using the following definitions for rating severity will be used:

- Mild – easily tolerated, causing minimal discomfort, and not interfering with normal everyday activities.
- Moderate – sufficiently discomforting and may interfere with normal everyday activities.

- Severe – incapacitating and/or preventing normal everyday activities.

A Serious Adverse Event (SAE) is any adverse device experience that results in any of the following outcomes: death, a life-threatening adverse device experience, in-patient hospitalization or prolongation of hospitalization, a persistent or significant disability/incapacity, or a congenital anomaly/birth defect. Important medical events that may or may not result in death, be life-threatening, or require hospitalization may be considered a serious adverse device experience when, based upon appropriate medical judgment, they may jeopardize the subject or subject may require medical or surgical intervention to prevent one of the outcomes listed in this definition

If any of the above adverse events are serious as defined by the FDA Code of Federal Regulations (CFR), Title 21, special procedures will be followed. All serious adverse events will be reported within 24 hours of acknowledgment to the Sponsor whether or not the serious events are deemed sampling session-related. All serious event reporting will adhere to 21 CFR part 812 and the IRB will be notified accordingly.

The SAE information will be entered into the database and a desk copy of the complete SAE report will be submitted to the study file.

Adverse events, whether serious or non-serious, will be followed until the condition is resolved, stabilized, otherwise explained or the subject is lost to follow-up. Adverse events will be captured throughout the study and where appropriate, medical tests and examinations will be performed to document the resolution of event(s). Outcomes may be classified as resolved, improved, unchanged, worse, fatal, unknown or lost to follow-up. Following the resolution of any study-associated adverse events there will be no further adverse event reports for that subject.

Reporting Adverse Events:

Report	Submit To	Description/Constraints
Adverse Events, Unanticipated Adverse Device Effect	IRB and Sponsor	If an unforeseen complication is determined to be an unanticipated adverse device effect, the investigator's report must be submitted within 10 working days after the investigator first learns of the effect.
Serious Adverse Events	IRB and Sponsor	The sponsor must be notified within 24 hours of serious adverse events. The IRB must be notified within 1 working day of serious adverse events as defined by FDA guidelines.

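### Probable and Highly Probable both require a known response pattern, so a new effect with plausible timing and no other explanation fits none of the five causality levels

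*Combined protocol and SAP*

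**What the plan says.** Section 14.0 has site staff review each adverse event and "assess its relationship to the study device (not related, unlikely, possible, probable, and highly probable", with a fixed definition for each level:

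- *Not related*: a cause other than the device is plain, for example the subject's own condition, another treatment or a concomitant drug.
- *Unlikely*: "The event was most likely produced by other factors such as the subject's clinical state", and in addition the event "does not follow a known response pattern to the investigational product".
- *Possible*: reasonable timing, a known pattern, or both; and in every case the event "could have been produced by other factors".
- *Probable*: three conditions joined by *and*. The timing is reasonable, the event "follows a known response pattern to the investigational product", and other factors give no reasonable explanation.
- *Highly Probable*: the same three conditions plus one of four supporting features. The event "either occurs immediately following investigational product administration", or improves once the product is stopped, or recurs when it is given again, or there is a reaction where it was applied.

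There is no level for events that cannot be assessed and no rule for an event that meets none of the definitions. The term for a known pattern is not defined. The list of potential effects in section 2.14 is its natural reference, but section 14.0 does not point to it.

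The protocol does expect new effects. Section 3.2 accepts that some side effects may still be unknown. The reporting table in section 14.0 has a line for them: "If an unforeseen complication is determined to be an unanticipated adverse device effect", the investigator must report it within 10 working days.

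**The concern.** The two upper levels mix two separate questions: whether the device caused the event, and whether the event was already expected of the device. A new effect fails the second question by its nature. Because the second question is a mandatory condition, the effect cannot reach Probable or Highly Probable however strong the causal evidence. The three lower levels do not take it in either, because each needs another cause.

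At stake is the quality of the relatedness rating for the events where it is most informative. Section 4.0 calls the device investigational because it may be used outside its cleared instructions, and section 2.7 allows up to 5 treatments per subject, so evidence from repeat exposure can arise. As written, that evidence cannot lift the rating of an unfamiliar event.

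**Working it through.** The plan gives no figure to reproduce; this is a check of definitions. Each event is described by four attributes taken from the wording of section 14.0:

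- T: timing is reasonable (yes/no)
- K: response pattern is known (yes/no)
- O: other factors are clearly the cause / most likely the cause / could be the cause / cannot reasonably explain the event
- X: at least one of the four supporting features is present (yes/no)

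This gives 2 × 2 × 4 × 2 = 32 combinations. The definitions become:

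- Not related: O = clearly
- Unlikely: O = most likely, and not K
- Possible: (T or K), and O = could or most likely
- Probable: T and K, and O = cannot
- Highly Probable: T and K, and O = cannot, and X

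**Step 1: the event in question.** Set T = yes, K = no, O = cannot.

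| Level | Condition that decides | Met? |
|---|---|---|
| Not related | other factors clearly the cause | no |
| Unlikely | other factors most likely the cause | no |
| Possible | other factors could be the cause | no |
| Probable | known pattern | no |
| Highly Probable | known pattern | no |

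None of the five levels fits.

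**Step 2: supporting evidence.** Setting X = yes changes nothing, because X is added to the known-pattern condition and does not replace it. Immediate onset and recurrence on repeat exposure are both without effect on the rating.

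**Step 3: all combinations as written.** Those with no level are:

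| T | K | O | X | Count |
|---|---|---|---|---|
| yes | no | cannot | yes or no | 2 |
| no | yes | cannot | yes or no | 2 |
| no | no | cannot | yes or no | 2 |
| no | no | could | yes or no | 2 |

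That is 8 of 32. Only the first row, 2 combinations, is the problem described here. The other 6 lack plausible timing and are a different matter. These are counts of logical cases and say nothing about how often such events occur.

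**Step 4: delete K from the two upper levels.** The first row becomes Probable when X = no, and meets Probable and Highly Probable when X = yes. The number with no level falls from 8 to 8 − 2 = 6, all without plausible timing.

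**Step 5: where the rating is used.**

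| Use | Depends on the rating? |
|---|---|
| Recording of events from first treatment (14.0) | no |
| Serious events to the sponsor within 24 hours (14.0) | no, sent whatever the relatedness |
| Sponsor review of all documented events (2.14) | no, covers every event |
| Safety summary (2.15.6) | no split by relatedness stated |
| Side effect criterion (2.15.1) | refers to adverse events, not to related ones only |
| Unanticipated device effect (14.0) | needs a finding that the device caused the event; no stated link to the scale |

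**The case against.** The best reply is that nothing stated in the plan turns on the rating, as step 5 shows. A down-rated event is still recorded, counted and seen by the sponsor, and a serious one is still reported. This stands, and it rules out several stronger readings.

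- A reader might infer that the gap distorts the side effect profile used as a success criterion. The text does not support this: neither sections 2.15.1 nor 2.15.6 restricts that profile to related events.
- A reader might infer that the gap delays the 10-working-day report. That period runs from the investigator's awareness of the effect, and no text makes Probable or higher a precondition. The rating is natural support for the finding but is not shown to control it.
- A reader might say that the scale itself directs sites to Possible or Unlikely. It does not, since both need another cause. Under-rating is a prediction of what a site does when no level fits.
- A reader might cross timing with known pattern for events without another explanation and report 3 of 4 cells empty. Two of those three lack plausible timing, so only one bears on this point.

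It can also be said that investigators will use judgment, or will read the known pattern loosely, for example by analogy with similar shockwave treatment. That would rescue some events. But the definitions are prescribed for use, the term is undefined, and 2 centers judging without a rule may differ. Sponsor review is a real safeguard but a partial one: section 2.14 frames it around regulatory reporting and does not say that the reviewer may re-rate relatedness.

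**Conclusion.** The concern holds in a narrow form. By the wording of section 14.0, an event with plausible timing, no other reasonable explanation and no known pattern has no valid level, whatever the evidence from onset or repeat exposure. The consequence is a missing or possibly too low relatedness rating, and weaker support for recognising an unanticipated adverse device effect. Adverse event counts, serious event reporting and the success criterion are not shown to be affected.

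Two assumptions matter. First, an event that other factors cannot reasonably explain is taken as one that they could not have produced. If the wording of Possible is read so loosely that almost any cause qualifies, the event lands in Possible, below an event with the same timing and evidence but a familiar pattern. The gap then becomes an under-rating. Second, the known pattern is taken to exclude effects that are new in type. The logic is certain under these readings; how sites would behave is an inference, and the documents give no basis for a frequency.

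This should be corrected. It does not threaten the planned analysis.

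**What to change.** In section 14.0, delete the known-pattern condition from Probable and Highly Probable. Probable then requires reasonable timing and no other reasonable explanation; Highly Probable requires both plus one of the four supporting features already listed. Do not borrow the *and/or* from Possible: it would let an event with a known pattern but no plausible timing be rated Probable.

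Record expectedness, on or off the section 2.14 list, as a separate item. The adverse event form is not among the documents, so this is needed only if the form does not already carry it. Expectedness and relatedness together can then inform the unanticipated device effect determination.

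The cost is two edited definitions, possibly one added form item, and the IRB approval that section 21.0 requires for any revision. The downside is that some events will be rated Probable or Highly Probable that would otherwise be rated lower. The change does not give a level to the 6 combinations without plausible timing, which lie outside this point.

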2.10 Biopsy Portion of the Study

- Subjects may enroll in the biopsy portion of this study. If the subject has signed the biopsy consent form and enrolled, the following will also be performed:
 - Biopsies may be taken from a treated area the day of treatment and/or may be taken 1, 3, 7 (+/- 1 day), 14 (+/- 2 days), 21 (+/- 2 days), and/or 30 days (+/- 3 days) post last treatment. A control will also be taken on the contralateral side of the treatment area.
 - Biopsy subjects may receive up to 6 biopsies.
 - A local anesthetic, such as lidocaine, may be injected to the area prior to biopsy.

- A 2 mm or 3mm punch biopsy (based on Physician assessment) will be taken from the treatment area.
- Sutures may be used to close the incision site.
- The subject may be asked to attend a 1 week (7-14 days) post each biopsy visit to remove the sutures and assess side effects.
- The following post biopsy treatment instructions will be reviewed:
 - Slight redness, initial tenderness to the wound site is normal; however, if you experience more redness, swelling, pain, pus, or drainage contact the study site immediately.
 - If the biopsy site begins to bleed, apply direct pressure for 10-20 minutes. If it continues to bleed, call the study site immediately.
 - Keep the wound dry today and remove bandage in 24 hours and leave off.
 - Avoid hot tubs, pools, and ocean until sutures are removed. Avoid soaking in water until 14 days after your biopsy.
 - When showering, wash carefully and do not scrub or traumatize the treated skin, or allow spray of shower to strike the skin directly. If the skin is treated harshly, this can increase the risk of scarring.
 - After showering, lightly pat dry the wound or let it air dry, then cover the biopsy site with an application of Vaseline (or petroleum jelly) at least 1-2 times daily. Keeping the wound moist reduces infection, minimizes scarring, and prevents crust formation over the wound.
 - Band-Aids (or any generic Adhesive Bandages) may be used for sleeping or in daily routines where the area may be rubbed/irritated. Whenever possible, keep Band-Aid (or generic Adhesive Bandage) off of the area and keep the area moist with Vaseline (or petroleum jelly) as previously described but do not allow drying out and forming a hard scab.

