2.14 Adverse Event Recording

All data captured must be supported by the Investigator's timely assessment and documentation of the adverse event in the case report forms or source documents. All documented adverse events will be reviewed by the Sponsor or designee to determine whether the adverse event meets regulatory reporting requirements and to ensure timely adverse event reporting to meet local and global regulatory requirements. All adverse events must be followed until their resolution.

Adverse Events Pertaining to the SoftWave Device:

Potential adverse effects associated with shock wave treatments include those listed below:

- Transient moderate increase in pain
- Redness and swelling
- Hematoma and petechial hemorrhage
- Headaches and fainting during extracorporeal shock wave treatments
- Short-term hypoesthesia
- Nausea during therapy
- Tingling during therapy

Adverse Events Pertaining to the Marker:

Using a marker has minimal risks and may produce effects on the body such as redness or a rash.

Adverse Events Pertaining to Ultrasound Gel:

The gel is a water-based gel that may be placed on the skin during treatment. No known adverse events are documented. However, an allergic reaction is always possible when placing a topical gel onto the skin. Allergic reaction may include a mild reaction such as skin redness, irritation, or hives.

Biopsies

Complication with biopsies can include pain, redness, swelling, infection, bleeding, scarring and skin texture irregularities.

Lidocaine

You may experience pain and numbness at the site of the injection. You may also experience redness, rash, infection, skin damage or nerve damage at the site of the injection. You may experience temporary loss of sensation and muscle function at the site of injection.

1% lidocaine (Lidocaine) with Epinephrine Injection

Lidocaine with epinephrine contains the preservative sodium metabisulfite which may cause allergic-type reactions including anaphylactic symptoms such as itching, hives, swollen areas of the body, and/or trouble breathing and life-threatening or less severe asthmatic episodes in certain susceptible people.

Other Cautions:

Incomplete response or no response may occur since some subjects may not respond to treatment.

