2.15.3 Patient Populations

Interim results may be collected and reported. All data will be analyzed at the end of the study on a per device basis as well as overall. The primary analysis will be performed by the intention-to-treat approach. Everyone who begins the treatment is part of the study whether he or she completes the study or not. Additional per-protocol analysis may also be performed on subjects who complete the entire clinical trial according to the protocol. The most appropriate method of handling missing values will be chosen based on the individual trial goals, endpoints and context.

The analysis of demographic, medical history, and efficacy variables will be based on all patients who are randomized and receive at least one treatment. The analysis of safety data will be based on all patients who are randomized, receive at least one treatment, and have at least some safety data.

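### The protocol's own SAE definition is limited to device experiences and is not reconciled with the other standards it cites; separately, causality is rated only against SoftWave, so biopsy, anaesthetic and comparison-device events have no rating of their own

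*Combined protocol and SAP*

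**What the plan says.** Section 14.0 defines the term as follows: "A Serious Adverse Event (SAE) is any adverse device experience that results in any of the following outcomes". Its provision for important medical events has the same limit: such an event "may be considered a serious adverse device experience when, based upon appropriate medical judgment" it may jeopardise the subject or call for intervention.

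The next paragraph starts special procedures on a different standard: "If any of the above adverse events are serious as defined by the FDA Code of Federal Regulations (CFR), Title 21". It then requires a report to the sponsor within 24 hours "whether or not the serious events are deemed sampling session-related". The reporting table at the end of section 14.0 uses a third formulation, seriousness under FDA guidelines.

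On causality, section 14.0 asks for the relationship to the study device and adds: "The following definitions will be used for rating relationship to the SoftWave treatments". The upper categories are worded in terms of the investigational product.

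The study exposes subjects to more than SoftWave:
- Section 2.10 offers an optional biopsy portion ("Biopsy subjects may receive up to 6 biopsies"), with local anaesthetic permitted and a control biopsy from the contralateral side.
- Section 2.14 foresees harm from these procedures ("Complication with biopsies can include pain, redness, swelling, infection, bleeding, scarring and skin texture irregularities"). For lidocaine with epinephrine it lists anaphylactic and life-threatening asthmatic reactions.
- Sections 2.1 and 4.0 allow treatment with a second shockwave device.

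On analysis, section 2.15.3 says: "All data will be analyzed at the end of the study on a per device basis as well as overall".

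**The concern.** There are two separate defects.

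The first concerns which events count as serious. A punch biopsy or a lidocaine injection is not an experience of a shockwave device. A site that applies the protocol's own definition could reasonably decide that a serious wound infection or anaesthetic reaction is not an SAE, and so not start the 24-hour clock. A site that applies the FDA wording might decide otherwise. Two sites could then count the same event differently.

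The second concerns attribution. The plan adds a biopsy procedure, an anaesthetic and a second device, but keeps a relationship scale with one target. The data would show that an event was thought unrelated to SoftWave, but not whether another part of the study caused it. For a comparison device that may be used in the same subjects, that is the information a per-device safety summary needs.

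**Working it through.** No planned figure is involved. The check sets the text of section 14.0 against the exposures in sections 2.1, 2.10, 2.14 and 4.0.

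**Step 1. Each cause against the two rules, read literally.**

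| Cause of event | Within the section 14.0 SAE definition? | Own relationship rating? |
|---|---|---|
| SoftWave | Yes | Yes |
| Comparison device | Yes; the definition names no particular device | No |
| Biopsy | Not on the literal wording | No |
| Local anaesthetic | Not on the literal wording | No |

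The clearest biopsy case is the contralateral control. If that side is untreated, which the word control implies but section 2.10 does not state, a serious infection there is not a device experience on any ordinary reading.

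**Step 2. Does the 24-hour rule close the gap?** Only in part. It applies regardless of relationship, but only to an event already classed as an SAE, and the relationship it sets aside is to a *sampling session*. That term is not defined. Its only other use is inside the Possible category of the causality scale. The other deadline in the reporting table, 10 working days, is tied to unanticipated device effects. A foreseen biopsy or anaesthetic complication is neither unanticipated nor a device effect.

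**Step 3. Where does the causality scale send these events?** Not related covers events clearly due to other factors, with therapeutic interventions and concomitant medications among the examples. An event clearly caused by the biopsy, the anaesthetic or the other device therefore goes there. One most probably so caused goes to Unlikely, provided it does not match a known SoftWave response. Pain, redness and swelling are on both the SoftWave and the biopsy lists in section 2.14, so an ambiguous local reaction at a treated and biopsied site can also be rated Possible. In no case is the actual cause recorded on the scale.

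**Step 4. Does this affect a planned output?** Section 2.15.3 promises results per device and section 2.15.6 summarises adverse events by treatment group. Section 2.1 lets a SoftWave subject also receive the second device. For such a subject, a SoftWave-only rating does not assign an event to the other device.

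**Step 5. Exposure.** Inputs: at most 6 biopsies per biopsy subject (section 2.10) and at most 50 subjects (section 2.1). Ceiling: 6 × 50 = 300 biopsies. The biopsy portion is optional and its enrolment is not stated, so the range is 0 to 300. The numbers of anaesthetic injections and comparison-device sessions are also not given.

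**The case against.** The strongest reply is that section 14.0, read as a whole, intends serious events to be reported whatever their cause. If an SAE already had to be due to the device, a clause requiring reports regardless of relationship would have little work to do, and the references to Title 21 and FDA guidelines may well be broader. In addition, section 14.0 has all adverse events recorded from the first treatment, and section 2.14 has the sponsor review every documented event for regulatory reporting. Much of this stands. A reader might infer that serious biopsy or anaesthetic events would disappear from the safety data, and the documents do not support that. What is at risk is SAE classification and the 24-hour report. The sponsor's review comes after documentation and sets no 24-hour clock for the site. The outside definitions are not reproduced, so their breadth cannot be judged from the documents.

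A reader might also infer that serious comparison-device events escape SAE reporting. They do not: any device experience is covered, and for that device only the causality point holds.

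Nor does the text support a distorted success criterion. Section 2.15.1 judges the adverse event profile as a whole, and section 2.15.6 tabulates events without filtering on relatedness or seriousness.

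Finally, rating a biopsy event as not related to SoftWave is a correct answer to the question the scale asks. That is fair; the fault is that no second question is asked.

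**Conclusion.** The concern holds in two limited parts. First, the protocol's own SAE definition is device-limited and is not reconciled with the Title 21 and FDA-guideline standards or with the sampling-session wording. A serious biopsy or anaesthetic event can therefore be left unclassified as an SAE and miss the 24-hour report. Second, the causality scale has one target, so events from the biopsy, the anaesthetic or the comparison device have no rating of their own, and the per-device analysis cannot attribute events in subjects who receive both devices.

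The size cannot be estimated from the documents. The 300 biopsies are a ceiling that requires every subject to join an optional portion and have the maximum number, and serious events are probably few. The first part rests on a literal reading of *device experience*. The second needs no such assumption, but its effect on the per-device analysis depends on the comparison device actually being used in subjects who also receive SoftWave.

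**What to change.** 1. In section 14.0, define an SAE as any untoward event that meets one of the listed outcomes, regardless of cause. State that this one definition governs the special procedures, the 24-hour rule and the reporting table, and align section 2.14 with it.
2. Delete *sampling session* in the 24-hour rule and in the Possible category, or replace it with a defined term.
3. On the adverse event CRF, rate relationship separately to SoftWave, to the comparison device and to the biopsy and anaesthetic procedure.
4. In section 2.15.6, tabulate adverse events by these attributions, so that the per-device summary can be produced for subjects who receive both devices.

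The cost is one revised definition, a few extra CRF boxes and one more table layout. A few more events may be counted as SAEs. Treatment, visits and sample size do not change.

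### Section 14.0 ends adverse event reporting for a subject, rather than for an event, once a study-associated event resolves, which contradicts the protocol's own capture and serious-event rules

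*Combined protocol and SAP*

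**What the plan says.** The sentence at issue ends the Section 14.0 paragraph on follow-up and outcome of adverse events: "Following the resolution of any study-associated adverse events there will be no further adverse event reports for that subject". Two sentences earlier the same paragraph says: "Adverse events will be captured throughout the study".

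Other parts of Section 14.0 set the duties this sentence meets:

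- Recording: "All adverse events that occur, starting from the time of the first treatment, will be recorded".
- Follow-up: each event is "captured and followed until the condition resolves, stabilizes, is otherwise explained, or the subject is lost to follow-up".
- Serious events: "All serious adverse events will be reported within 24 hours of acknowledgment to the Sponsor", whether or not they are judged related. The reporting table repeats this ("The sponsor must be notified within 24 hours of serious adverse events") and gives 1 working day for the IRB.
- Unanticipated effects: "If an unforeseen complication is determined to be an unanticipated adverse device effect", the investigator has 10 working days to report it.

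Outside Section 14.0, adverse events are documented after treatment (2.8) and at follow-up visits (2.9). They are assessed in every visit column of the schedule (2.13, Schedule of Visits and Procedures). The safety analysis draws on events collected over the whole study (2.15.6).

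**The concern.** An end-of-reporting rule normally applies to an event. This one applies to a person. Once it takes effect, its words leave no route for a later event in that subject to be reported, whether a recurrence, a biopsy complication, a serious event or an unanticipated device effect.

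Collection of adverse events is the safety objective (1.2), and a side effect profile acceptable to the Physician is one of the success criteria (2.15.1). If sites applied the sentence as written, that judgement would rest on a record that stops early in exactly those subjects who have already had an event. Separately, a site facing a serious event in such a subject would hold two instructions from the same section that cannot both be followed.

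**Working it through.** The plan states no figure on this point, so there is none to reproduce. The check is a comparison of texts, plus one calendar calculation from the protocol's own intervals.

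**Step 1: scope of the sentence.** Trigger: resolution of study-associated events. Object: the subject. Time limit: none. Exceptions: none. Reading *any* as *all* only delays the trigger; a new event after all earlier ones have resolved is still shut out.

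**Step 2: side by side.**

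| Rule | Place | Compatible with the sentence as worded? |
|---|---|---|
| Record all events from first treatment | 14.0 | No, if reports include recording |
| Capture throughout the study | 14.0, 2.15.6 | No, if reports include recording |
| Document or assess at each stage | 2.8, 2.9, 2.13 schedule | No, if reports include recording |
| Serious events: sponsor 24 hours, IRB 1 working day | 14.0 text and table | No; both concern reports |
| Unanticipated device effects: 10 working days | 14.0 table | No; both concern reports |

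**Step 3: possible meanings.**

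- *Literal.* Later events in the subject are not reported. All the conflicts above apply.
- *Closes follow-up of the resolved event only.* Nothing is lost, but the sentence names the subject.
- *Ends reporting once all events have resolved after the last visit.* Nothing is lost during the study, but the sentence does not mention the last visit or study exit.
- *Limits submissions to the IRB and sponsor only.* Case report form data and the 2.15.6 summary are intact. The last two rows of the table still conflict.

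The vocabulary does not decide between these. Section 14.0 also says "Each adverse event reported will be graded on a 3-point severity", where the term covers adverse events in general and not only formal submissions.

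**Step 4: how early the trigger could come.** Section 2.5 tells subjects to expect mild soreness or stiffness over 48 hours. Section 2.7 allows up to 5 treatments, 3 to 14 days apart. Since 48 hours is shorter than 3 days (72 hours), such a reaction could resolve before the second treatment. With 5 treatments and a 90-day visit, the time from first treatment to last visit is

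- shortest: 4 × 3 + 90 = 102 days;
- longest: 4 × 14 + 90 = 146 days.

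Taking off 2 days leaves 100 to 144 days, with up to 4 further treatments and any biopsies, after the literal cut-off. This assumes that the reaction is recorded as a study-associated event. Section 2.5 calls it normal, so it might not be.

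**Step 5: which summaries would move under the literal reading.**

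- *Overall percent with at least one event:* unchanged. A subject can be closed only after an event that has already been counted.
- *Percent with a particular event type:* understated when its first occurrence in a subject falls after closure.
- *Per-device percent with at least one event:* can be understated. Section 2.1 lets a subject receive the comparison device as well, and 2.15.3 analyses data by device. If x of n subjects on a device have an event, and m of those x were already closed by a resolved event on the other device, the report shows (x − m)/n instead of x/n. The documents give neither m nor the number of subjects who receive both devices.

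**The case against.** The strongest reply is context. The sentence closes a paragraph about following existing events to an outcome, and that paragraph itself requires capture throughout the study. A site reading all of Section 14.0 would probably take the sentence as ending follow-up of a finished event, or as ending reporting once everything had resolved. There are safeguards too. Section 2.14 has the sponsor or its designee review every documented event for regulatory reportability, and Section 5.0 provides for case report form review and periodic monitoring. If only submissions were limited, the event would still be on the form, and the main exposure would be a late report.

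Much of this stands. It makes the literal outcome less likely. A reader might infer that sites would in fact stop reporting serious events, but the documents do not support that, because the other rules remain in force and are worded as obligations. The reply does not remove the defect, however. Sponsor review reaches only events that were documented, and a report found later at monitoring can already have missed the 24-hour, 1-working-day or 10-working-day limit. No text tells the site which of the conflicting instructions governs.

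**Conclusion.** The concern holds as an internal contradiction that should be fixed. One sentence in Section 14.0, as worded, ends reporting for a subject with no exception, against the recording, capture, assessment and expedited reporting rules. The conflict with the serious-event and unanticipated-effect rules persists even if the sentence limits only submissions to the IRB and sponsor.

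The size of any loss cannot be computed: the documents give no event rates, no resolution times for recorded events and no count of subjects treated with both devices. A reader might infer that all reported adverse event percentages would be too low. That goes too far: under the literal reading the overall percent with any event is unchanged, and the possible understatement lies in particular event types and in per-device percentages. Nor can it be said that the Physician's judgement would change, since Section 2.15.1 sets no numerical limit for adverse events. If the sentence was meant only to close a resolved event, or to apply after the last visit, nothing is lost except clarity.

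**What to change.** Replace the sentence with wording such as:

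> Reporting on an individual adverse event ends when that event has resolved or stabilised, has been otherwise explained, or the subject has been lost to follow-up. New events, including recurrences, are recorded and reported for every subject through the last study visit. Serious adverse events and unanticipated adverse device effects are always reported.

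If the intention was to limit only submissions to the IRB and sponsor, say so, and keep the last sentence.

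At the same time, reconcile the follow-up end point in Section 2.14, which names resolution only, with Section 14.0, which also accepts stabilisation, another explanation or loss to follow-up.

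The cost is a wording amendment with written IRB approval under Section 21.0; it adds no visits or forms. The reported profile may be less favourable than under the literal rule.

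The rule in Section 12.0 that stops data collection after withdrawal bears on events still open at that time. It should be handled as a separate point, because changing it may need further contacts or consent wording, and its cost is not assessed here.
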